This is an open label trial. Treatment will be conducted on either the left or right knee, thigh, arm, or ½ the abdomen, depending upon which area has the most cellulite or skin laxity. The contra-lateral side will not be treated and will serve as a control. A comparison of baseline photographs (prior to treatment) to photographs taken 1, 3 and 6 months after the completion of treatment will be conducted. Photographic equipment and the protocol for photography will be consistent at each visit. Ultrasound may be taken at baseline and at the follow-up visits to evaluate flatness of cellulite and dermal fibrosis or enlargement of the reticular dermis. Non-invasive light measurements may also be taken at baseline and follow-up visits. These do not hurt or pose a risk to the subjects and are similar to shining a flashlight on the skin and measuring the light. The area treated will be measured with a tape measure, weight/height will be recorded and the Body Mass Index (BMI) will be calculated at baseline and follow-up visits. In addition, skin elasticity may be measured at the treatment areas at baseline and follow-up visits. The photographs, ultrasound and measurements will be taken using consistent procedures at each visit by viewing the baseline photograph and using landmarks such as freckles and birthmarks.

The laser system to be used in this clinical study, Candela GentleYAG, a 1064 nm Nd:YAG laser is a commercially available laser and has been cleared by FDA under K022923, K022951, K023193 and K033172.

The Candela GentleYAG is cleared for removal of unwanted hair, for stable long term or permanent hair reduction and for treatment of pseudofolliculitis barbae, and is indicated on all skin types Fitzpatrick I-VI including tanned skin. The GentleYAG is cleared for treatment of vascular lesions such as port wine stain birthmarks, telangiectasia, rosacea, and leg and spider veins, and is cleared for treatment of benign pigmented lesions such as lentigos (age spots), café au lait birthmarks, and tattoos. The laser is also indicated for treatment of red pigmentation in scars with vascularity, and for treatment of wrinkles.

The Candela DCD produces a brief, timed spray of cryogenic fluid that evaporates from the skin surface and cools the epidermis, prior to each laser pulse. The DCD has been cleared by the FDA for minimizing pain and cooling the epidermis during laser treatment (K953412). The DCD is part of the Candela GentleYAG laser system.

Treatment Procedure

The following table provides a summary of the required study visits, the procedures and assessments to be performed at each visit.

Assessments/ Procedures	Pre- Tx	Tx 1	Follow-up 1 month	Follow-up 3 months
Informed Consent	X			
History	X			
Inclusion/ Exclusion Criteria	X			
Subject No. Assignment Randomization	X			
Photography	X	X	X	X
Ultrasound/skin elasticity assessments (optional)	X	X	X	X
Non-invasive light measurements	X	X	X	X
Measurement (average of 3) / Weight	X		X	X
Laser treatments		X		
Assessments of side effects		X	X	X
Post-treatment care instructions		X		
Assessment			X	X
Subject Satisfaction survey			X	X

Pre-Treatment Procedure

- 1. Subjects will be recruited at the investigational site.
- 2. Prior to any screening assessments, informed consent will be obtained. When the subject fully understands the possible benefits and risks of the study, the subject will be asked to sign and date the informed consent form. The investigator will then sign and date the form. The subject will be given a copy of the completed consent form.
- 3. A detailed medical history will be obtained.
- 4. The subject will undergo a standard exam to determine if they meet the study criteria.
- 5. Skin type will be recorded using the Fitzpatrick classification of phototype.
- 6. Tape measurements of the treated area, height, and weight will be recorded.
- 7. The presence and severity of cellulite will be noted using the following 2 methods:

Nurnberger-Muller Scale:

- Stage 0: No dimpling. Pinch test "folds and furrows", no mattress like appearance.
- Stage 1: No dimpling. Pinch test reveals mattress like appearance.
- Stage 2: Dimpling spontaneously standing.

Stage 3: Dimpling spontaneously standing and lying down.

Texture Scale:

Hard or Solid: Pinch test "firm folds and furrows" mattress-like appearance. Adherent to deep planes. Not modified with lying versus standing position.

Soft or Flaccid: Pinch test "spongy and floating folds and furrows", mattress-like appearance. No adherence to deep planes. Not painful, flaccid. "Orange peel skin" appears spontaneously.

Edematous: Doughy consistency. Dimpling Spontaneously. Pain and cramps. Signs of venous and lymphatic insufficiency "legs in boot/column".

- 8. The pre-treatment photographs will be obtained using the Canfield Monostand device. This device will keep the ambient lighting, background, camera settings exactly the same for each scheduled photograph during the study. Photographs will be of the treated and control areas.
- 9. Optional: Imaging of skin via a non-invasive high frequency ultrasound imaging device may be performed
- 10. Optional: Measurement of skin elasticity using non-invasive instrumentation may be performed.
- 11. Just prior to treatment, the subjects will be assigned a study subject number. These numbers will be assigned consecutively.

Laser Treatment:

[figure not shown]
One laser treatment will be performed, and the procedure will be as follows:

- 1. The treatment area will be photographed prior to the treatment. Emphasis will be placed on keeping the ambient lighting, background, camera settings exactly the same for each scheduled photograph during the study.
- 2. Tape measurement and weight will be recorded.
- 3. The treatment area will be comprised of the arm (circumferential upper arm area), knee (approximately 10cm circumferentially around the patellar bone), entire thigh (from the upper lateral areas of the thighs inner to outer area excluding hips moving downwards until just above the knee), or abdomen (from the costal margin to just superior to the pelvic bone).
- 4. Topical anesthetic may be applied to the skin according to the manufacturer's instructions if the subject requires it or if the doctors feels the subject might not tolerate the treatment with out the use of topical anesthetic
- 5. Starting with the selected diameter spot size handpiece, test spots may be conducted with the laser at a low fluence until the optimum fluence is achieved (prior to intolerable discomfort or a reaction of mild redness or edema is visible).
- 6. Laser treatment will include up to six (6) consecutive passes of the laser over the treatment area. The treatment parameters are noted in the following table.

Parameter	Parameter Value Range		
Spot size diameter:	10-22 mm		
Wavelength	1064 nm		
Fluence:	10-50 J/cm ²		
Laser pulse duration:	20-50 ms		
Rep. rate:	Up to 2 Hz		
DCD cooling	0-50ms		

Immediate Post-Treatment Procedure

1. Immediately after treatment the subject will be asked to rate the pain on a 0-10 (none to worst).

3. The subject will be instructed on post-treatment care.

Long Term Follow-Up Procedure

- 1. Subjects will return to the study site for a one (1), three (3) and (6) month follow-up visits after the laser treatment.
- 2. The treatment areas will be photographed.
- 3. Tape measurements and weight will be recorded.
- 4. Ultrasound and skin elasticity measurements will be done if they were done at baseline.
- 5. A clinical evaluation of purpura, edema, erythema, hyperpigmentation, hypopigmentation, blistering and scarring will be assessed by the investigator using the following scale:

0 = absence

1 = mild

2 = moderate

3 = severe

- 6. At the follow-ups the subjects will be asked to evaluate their satisfaction with the treatments. They will be asked to complete the questions below. The first question will ask the subject to rate each treatment procedure using the following scale:
 - 1 = Not Satisfied
 - 2 = Little Satisfaction
 - 3 = Somewhat Satisfied
 - 4 = Satisfied
 - 5 = Very Satisfied
- 7. The subject will also be asked to rate the overall improvement in the appearance of their treated skin using the following scale:
 - 1 = No improvement
 - 2 = Little improvement
 - 3 = Moderate improvement
 - 4 = Significant improvement
 - 5 =Complete improvement
- 8. The subject will have the option to receive an additional treatment on the control side if the treatment results in asymmetric improvement of cellulite. They may have this option starting at the final follow-up.

SECTION 4: SUBJECTS (PERSONS/CHARTS/RECORDS/SPECIMENS)

A. Number of Subjects (Charts/Records/Specimens)

- Indicate the maximum number of subjects to be consented on this UCI protocol.
 - Include projected screen failures and early withdrawals.
 - For Mail/Internet surveys include the number of people directly solicited.
 - If the study involves use of existing charts, records, specimens, specify the maximum number that will be reviewed to compile the data or the sample population necessary to address the research question.

40

- 2. Of the maximum number of subjects listed above, indicate the **target sample size** for the study.
 - The target sample size is the number of subjects expected to complete the study or the number necessary to address the research question.
 - If the study only involves use of existing records, charts, specimens, specify the target number needed to address the research question.

24

Explain how the study sample size was determined (e.g., power analysis; review of related literature).

This is a pilot trial; therefore there is no basis for the sample size needed to determine a significant difference.

- 4. For multi-center research, indicate the overall sample size for the entire project (across all sites).
- [x] Not applicable This study is not a multi-center study.

B. Inclusion and Exclusion Criteria

1. Describe the **characteristics** of the proposed subject population (age, gender, health status, language, etc.)

Male or female \geq 18 years of age.

- 2. Provide the inclusion and/or exclusion criteria for the proposed subject population, as applicable.
- [] Not applicable This is not a clinical investigation and/or characteristics of the population sufficiently describe the proposed subject population.

Inclusion Criteria

- 1. Male or female \geq 18 years of age
- 2. Cellulite on the arm, knee, thigh or abdomen at stage 2 3 of cellulite per Nurnberger-Muller scale.
- 3. Subject is not overweight per B.M.I. criteria (B.M.I < 27).
- 4. Subject has Fitzpatrick skin phototype I-IV.
- 5. Subject is willing to participate in study and adhere to follow-up schedule.
- 6. Subject has signed the Informed Consent Form.

Exclusion Criteria

- 1. Subjects that have cellulite at stage 0-1 per Nurnberger-Muller Scale (the doctor will determine this)
- 2. Subjects that have had liposuction or other surgical procedures (including Mesotherapy) to remove fat on the proposed treatment area during the past year.
- 3. Subject has severe cellulite with referral to pain and/or tenderness on the area to be treated (Texture Scale: edematous).
- 4. Subject is overweight (BMI \geq 27).
- 5. Subject has known photosensitivity or history of ingesting medications known to induce. photosensitivity in the previous 3 months.
- 6. Subject has a personal or family history of keloid formation or of scarring.
- 7. Subject is pregnant or lactating.
- 8. Subject has a history of uncontrolled diabetes, and/or who requires medication which may interfere with the study.
- 9. Subjects with a known history of neuropathy.
- 10. Subjects with a known history of a coagulopathy.
- 11. Subject is unable or unwilling to comply with the study requirements.
- 12. Subject has a pacemaker or metallic implants.
- 13. Subject has Fitzpatrick skin type V and VI.
- 14. Subject is mentally incompetent or a prisoner.

3. If inclusion/exclusion is based on age, gender, pregnancy/childbearing potential, or race/ethnicity, provide a scientific rationale.

Pregnant women are more prone to hyperpigmentation of the skin in response to laser treatments of all types and thus, they will be excluded.

We will enroll Fitzpatrick types I-III because although the 1064nm laser is indicated for all skin types, previous studies using the 1064 nm laser have noted that skin types IV and V experience more pain during treatment and are significantly more likely to develop skin dyspigmentation.

SECTION 5: RECRUITMENT METHODS AND PROCESS

A. Recruitment Methods

Please check all applicable recruitment methods that apply to the study. Place an "**X**" in the bracket [] next to the recruitment method.

- [] This study involves no direct contact with subjects (i.e., use of existing records, charts, specimens)
 - Skip to Section 6.
- [x] UCI IRB approved advertisements, flyers, notices, and/or media will be used to recruit subjects.
 - Passive Recruitment Potential subjects initiate contact with the study team.
 - Complete Question 5B Explain where recruitment materials will be posted.
- [] The study team will recruit potential subjects who are unknown to them (e.g., snowball sampling, use of social networks, direct approach in public situations, random digit dialing, etc.)
 - Active Recruitment Researchers contact potential subjects.
 - Complete Question 5B.
- [X] The UCIMC Clinical Trials web page will be used.
 - Passive Recruitment Potential subjects initiate contact with the study team.
 - Skip to Section 6.
- [] The UCI Social Sciences human subject pool will be used.
 - Passive Recruitment Potential subjects initiate contact with the study team.
 - Skip to Section 6.
- [x] Study team members will contact potential subjects who have provided permission to be

contacted for participation in future research studies.

- Active Recruitment Researchers contact potential subjects.
- Complete Question 5B Explain when and how these individuals granted permission for future contact; provide the IRB protocol numbers, if applicable.
- [x] Study team members will approach their own patients, students, employees for participation in the study.
 - Active Recruitment Researchers contact potential subjects.
 - Complete Question 5B.
- [] Study team members will send UCI IRB approved recruitment materials (e.g., recruitment flyer, introductory letter) to colleagues asking for referral of eligible participants.*
 - Passive Recruitment Potential subjects initiate contact with the study team or
 - Active Recruitment Colleagues get permission from interested individuals to release contact information to researchers. Researchers contact potential subjects.
 - For Active Recruitment, complete Question 5B.
 - *Additional requirements for using this recruitment method are included in the Protocol Narrative instructions.
- [] Study team members will provide their colleagues with a UCI IRB approved introductory letter. The letter will be signed by the treating physician and sent to his/her patients to inform them about how to contact study team members.
 - Passive Recruitment Potential subjects initiate contact with the study team.
 - The IRB approved letter must be sent by the treating physician.
 - The study team does not have access to patient names and addresses for mailing.
 - Skip to Section 6.
- [] UCI study team members will screen UCIMC medical records to determine subject eligibility and approach patients directly about study participation.*
 - Active Recruitment Researchers contact potential subjects.
 - Complete Appendix T to request a partial waiver of HIPAA Authorization.
 - Complete Question 5B.

*Additional requirements for using this recruitment method are included in the Protocol Narrative instructions.

- [] Other Methods: <indicate the recruitment method(s) here>
 - Complete Question 5B, as applicable.

B. Recruitment Process

- 1. Based on the boxes checked above, describe and provide **details of the recruitment process** (i.e. when, where, by whom and how potential subjects will be approached).
- 2. If active recruitment methods will be used, explain how the individual's privacy will be protected.

Subjects interested in participation in the study will contact the clinical study team. During this first study contact they will be informed regarding the goals of the study, history of the investigational device, inclusion/exclusion criteria, study procedures, potential benefits, risks and duration of the study. No treatment or data collection will be obtained before a subject is enrolled. Subjects will provide consent prior to providing HIPAA-regulated Protected Health Information and enrolled after informed consent materials, including the specifics of research participation, the potential risks and benefits of participation, and confidentiality concerns, are presented.

Subjects who believe they meet the exclusion and inclusion criteria and remain interested in the study will be invited to come in for their screening visit. During the screening visit, the investigator will ask the subject questions in order to determine if the inclusion and exclusion criteria are met. Following the investigator's determination that the inclusion and exclusion criteria are met, the subject will be invited to participate in the study. No data about the subject will be recorded until informed consent and HIPPA Authorization have been obtained.

This study will be posted on clinicaltrials.gov

SECTION 6: INFORMED CONSENT PROCESS

Describe the specific steps for obtaining informed consent.

- Include information about when and where consent will take place and the length of time subjects are given to decide whether they wish to participate.
- If study team members will approach their own patients, students, or employees for participation in the study, explain what precautions will be taken to minimize potential undue influence or coercion, and how compromised objectivity will be avoided.

Check all that apply:

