- 4. Include a critical evaluation of existing knowledge, and specifically identify the information gaps that the project intends to address.
- 5. Describe previous research with animals and/or humans that provides a basis for the proposed research. Include references/citations, as applicable.

There are numerous therapies that have been advertised for the treatment of cellulite, but there is little scientific evidence that any of these treatments are beneficial. In fact, much of this evidence is subjective or based upon patient self-assessment. The objective of this investigation is to evaluate safety and effectiveness of a non-ablative treatment for cellulite in conjunction with skin tightening by increasing dermatofibrosis of the reticular dermis using the Candela GentleYAG laser.

Study outcome will be assessed as follows:

A panel of three independent, blinded individuals experienced in dermatological cosmetic therapy will determine percent improvement in cellulite appearance by comparing photographs taken at the pretreatment visit to those from the 1, 3 and 6 month follow-up visits. Each evaluator will be ask to compare the treated and non-treated areas on a blinded basis and then will rate improvement on the scale 0 to 4, as described below.

% Improvement Description		core
0%	No improvement	0
1-25%	Slight improvement	1
26-50%	Moderate improvement	2
51-75%	Significant improvement	3
76-100%	Complete improvement	4

The difference scores between the treated and the untreated sides will be used to measure treatment efficacy.

The investigator's assessments during follow-up visits will be tabulated and analyzed with basic descriptive statistical methods.

Ultrasound analysis, skin elasticity measurements and non-invasive optical measurements may also be performed prior to treatment and at the 1, 3 and 6 month follow-up visits to determine any changes in skin thickness.

Safety will be assessed by clinical evaluation of purpura, edema, erythema, hyperpigmentation, hypopigmentation, blistering and scarring. Assessments will be performed by the investigator using the following scale:

0 = absence 1 = mild 2 = moderate 3 = severe

SECTION 2: ROLES AND EXPERTISE OF THE STUDY TEAM

List all study team members below.

- Describe their specific role and responsibility on the study in the text box provided.
- 2. **Faculty Sponsors** list as Co-Researchers and describe their role on the project; include oversight responsibilities for the research study.

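### The protocol most naturally has severity pick the treated side, leaving the milder side as the only control; it lists randomisation without settling how left or right is chosen

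*Protocol*

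**What the plan says.** The study design paragraph (before Treatment Procedure) sets both the treated area and the control. It begins "Treatment will be conducted on either the left or right knee, thigh, arm", adds half of the abdomen as a further choice, and continues "depending upon which area has the most cellulite or skin laxity. The contra-lateral side will not be treated and will serve as a control". The same paragraph calls the trial open label and does not mention randomisation.

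The visit table under Treatment Procedure has a Pre-Tx row reading "Subject No. Assignment Randomization". The matching step, Pre-Treatment Procedure item 11, says only that subject numbers are given consecutively just before treatment.

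Section 1 has three blinded evaluators compare follow-up photographs with the pretreatment ones; each "then will rate improvement on the scale 0 to 4, as described below". It then states: "The difference scores between the treated and the untreated sides will be used to measure treatment efficacy".

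**The concern.** A within-subject comparison is credible when the two sides are exchangeable before treatment. If the worse side is treated by rule, they are not, and two things other than the laser can move the difference score.

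- **Regression to the mean.** A side picked because it looked worse will on average look less bad later, to the extent that the reading that picked it shares temporary, side-specific variation with the baseline photograph. This favours the laser.
- **Unequal baseline on a percent scale.** The same absolute change is a smaller percentage of a worse starting point. The direction of this effect is uncertain, and it may run against the laser.

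The untreated side is the only control, so the single efficacy comparison carries both effects. Choice of side is trial conduct: an analysis plan cannot make the sides comparable afterwards, and it can adjust only for baseline data that were recorded.

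**Working it through.** **1. The sections side by side.**

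- *Design paragraph.* The severity clause follows the choice of left or right, so its natural reading is that severity picks the side. The other reading takes area to mean body region, as Laser Treatment item 3 does when it defines the treatment area. On that reading the text shown does not say how left or right is chosen.
- *Visit table and item 11.* Randomisation is named once, beside subject numbering. Consecutive numbering does not allocate a side. If randomisation was meant to pick the side, the table conflicts with the natural reading of the design paragraph.
- *Order of steps.* Item 6 reads "Tape measurements of the treated area, height, and weight will be recorded", and item 8 photographs treated and control areas. Both come before item 11, which suggests that the side is already known when the number is given. List order is not proof.

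**2. Is there a figure to reproduce?** No. The target of 24 (maximum 40 consented) has no alpha, power, effect size or SD behind it, and Section 4A says so. The point does not depend on it.

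**3. What worse-side selection does, as illustration.** Every input below except n = 24 and the 0-4 bands is assumed. Per side, observed severity has variance 1, of which *r* is true severity. The left-right correlation of true severity is *ρ*. Error variance is 1 - *r*. A share *f* of that error variance is common to the reading that picks the side and the baseline photograph. Let v = *r*(1 - *ρ*) + (1 - *r*). With the worse side treated and no laser effect:

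- true baseline gap between sides = 2*r*(1 - *ρ*)/√(πv)
- spurious difference in change, continuous scale = 2*f*(1 - *r*)/√(πv)

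At *r* = *ρ* = 0.8, v = 0.16 + 0.20 = 0.36 and √(πv) = 1.063. The true gap is 0.32/1.063 = 0.30 SD whatever *f* is. The spurious difference is 0.40/1.063 = 0.376 SD at *f* = 1, 0.188 at *f* = 0.5, 0.094 at *f* = 0.25, and 0 at *f* = 0.

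**4. On the trial's own score.** The scale has a floor at no improvement and is banded 0, 1-25, 26-50, 51-75 and 76-100%. At *f* = 1 the floor alone roughly halves the spurious change, from 0.377 SD (simulated) to 0.188 SD. The simulation used 10,000 trials of 24 subjects per cell, *r* and *ρ* each in {0.7, 0.8, 0.9}, and mean severity of 3, 3.5, 4 or 5 SD. Rejection rates use a two-sided 5% paired t-test, which is also an assumption because the protocol names no test.

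| Share *f* | Points, mid case* | Rejections, mid case* | Points, all cells | Rejections, all cells |
|---|---|---|---|---|
| 1 | 0.286 | 37.1% | 0.162 to 0.434 | 16.9-58.2% |
| 0.5 | 0.128 | 11.2% | 0.062 to 0.205 | 6.8-17.0% |
| 0.25 | 0.054 | 6.4% | 0.013 to 0.090 | 5.1-8.4% |
| 0 | -0.023 | 6.0% | -0.045 to -0.001 | 4.7-6.0% |
| Side randomised | 0.002 | 5.0% | - | 5.0-5.4%† |

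*\*r = ρ = 0.8, mean 3.5 SD. †Four mean severities at r = ρ = 0.8.*

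The sign itself changes with *f*, and the protocol does not fix *f*. The model uses one reading per photograph, whereas the trial uses three raters.

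**The case against.** - **Unavailable text.** Text just before the design paragraph was not available to this review and could describe randomisation. This stands. A reader might infer that the protocol never describes randomisation, and the documents do not support that. What can be said is that the design paragraph, the visit table and item 11 do not agree as worded.
- **Unknown sharing.** The magnitude depends on *f*, and no section shown says who picks the side or from what reading. This also stands. The exam step, "The subject will undergo a standard exam to determine if they meet the study criteria", concerns eligibility, so it cannot be used to argue that examiner error is kept out of the baseline photograph, or that it enters. Standardised photography ("This device will keep the ambient lighting, background, camera settings exactly the same for each scheduled photograph during the study") limits variation from equipment but not real temporary variation in the skin.
- **Existing safeguards.** Raters are already blinded. Both sides are photographed at Pre-Tx, so imbalance can be seen and graded. The treated area is photographed again before the laser, which could show untreated change if the two visits are apart (the interval is not stated). It would therefore be wrong to say that the protocol leaves no means of examining selection. These safeguards do not remove a difference that exists before any rating.
- **Pilot status.** Section 4A makes no claim to detect a significant difference. That excuses the sample size. It does not make the sides comparable, and Section 1 states effectiveness as part of the objective.
- **Eligibility.** Randomising the side could assign the laser to a side below stage 2. This is a real cost and is carried into the fix.

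**Conclusion.** The point holds as a conflict to be reconciled with a consequence for interpretation. If severity picks the side, which is the more natural reading, the treated and control sides differ at baseline by rule, and the difference score cannot be credited to the laser alone.

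Its size and net direction cannot be determined from the document. The illustrative range is from slightly against the laser (-0.05 points) to 0.43 points in its favour, and the upper end requires all error to be shared between side selection and the baseline photograph.

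A reader might infer that the design inflates false positives to 58%. A continuous model without the floor, with full sharing, gives even more: about 30-85% for reliability 0.7-0.9 and correlation 0.7-0.95. Neither is supported as an estimate for this trial. Every driving input is assumed, the trial does not use an unfloored score, and with a quarter or less of the error shared the rates are close to 5%.

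It should be fixed. Confidence is medium because of the second reading of the design paragraph and the unavailable text.

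**What to change.** Reconcile the design paragraph, the visit table and Pre-Treatment item 11 so that they state how left or right is chosen.

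- **Preferred.** Choose the body region by severity. Then randomise left versus right within it from a concealed list, opened at the subject-number step after baseline photographs of both sides. Record the baseline severity grade and tape measurements for both sides, so that the difference score can be adjusted for them.
- **If the side is not to be randomised.** Remove randomisation from the visit table, describe the comparison as non-randomised, and do not attribute the difference score to the laser alone.

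The preferred route costs revised wording, a left/right list of 40 entries (the maximum consented) and second-side baseline records. It needs no extra visits.

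The downside is that some subjects will have the milder side treated. The offer of later control-side treatment (Long Term Follow-Up item 8) depends on asymmetric improvement and starts at the final follow-up, so it does not compensate everyone. The sponsor must also reconcile how the existing stage 2-3 criterion applies to each side; no eligibility rule is proposed here.

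### Stage 2 or 3 cellulite is not required on the treated area, which may be chosen for laxity, yet efficacy is scored only on cellulite

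*Protocol*

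**What the plan says.** **Choice of area.** The design description, ahead of the Treatment Procedure heading, says that one knee, thigh, arm or half of the abdomen is treated, "depending upon which area has the most cellulite or skin laxity". The opposite side is left untreated as the control.

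**Eligibility (Section 4B).** Inclusion criterion 2 reads "Cellulite on the arm, knee, thigh or abdomen at stage" 2 or 3 on the Nurnberger-Muller scale. Exclusion criterion 1 reads "Subjects that have cellulite at stage 0-1 per Nurnberger-Muller Scale (the doctor will determine this". Neither mentions the area that will be treated. The next two exclusions do: criterion 2 concerns procedures "to remove fat on the proposed treatment area during the past year", and criterion 3 concerns severe cellulite "with referral to pain and/or tenderness on the area to be treated".

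**Baseline staging (Pre-Treatment Procedure, item 7).** "The presence and severity of cellulite will be noted using the following 2 methods", one of which is the Nurnberger-Muller scale. The item does not say which region is staged. On that scale stages 0 and 1 both mean no dimpling; stage 1 shows its mattress-like look only on a pinch test.

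**Efficacy (Section 1).** Three blinded evaluators "will determine percent improvement in cellulite appearance by comparing photographs" from before treatment with those from follow-up, on a 0 to 4 scale. The treated-minus-untreated difference in that score is the efficacy measure. Skin elasticity, the measurement closest to laxity, is optional.

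**The concern.** Eligibility, choice of area and outcome should refer to the same piece of skin, and the text does not make them do so. Eligibility can be met on one region, treatment can go to another because it is lax, and the outcome then asks how far cellulite has improved there. If that region had no visible dimpling on either side, the photographs hold little or nothing for the panel to rate. The evaluators can give 0 to both sides, or give a score that reflects something other than cellulite.

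A subject of this kind says little about whether the laser improves cellulite. Tightening, the effect that led to the choice of area, is not captured by the efficacy score either. The pilot's estimate would be pulled toward no effect by the way areas were chosen, and it would be unclear whether it describes cellulite treatment, laxity treatment or a mixture.

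**Working it through.** The protocol gives no figure on this point to reproduce. The check is a side-by-side reading, followed by a simple dilution formula.

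**Step 1. Does the text permit the path?** Take a subject with stage 2 cellulite on the thigh and a lax upper arm at stage 0 or 1.

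| Rule | Applied to this subject |
|---|---|
| Inclusion criterion 2 | Met, by the thigh |
| Exclusion criterion 1, read for the subject as a whole | Not triggered; the subject has stage 2 cellulite |
| Exclusion criterion 1, read for the treated area | Triggered if the arm is chosen, but the wording does not say this |
| Exclusion criterion 1, read for any region | Triggered, but so would be anyone with stage 3 thighs and smooth arms, which is implausible |
| Choice of area | The arm is allowed, on the ground of laxity |
| Panel score | Cellulite improvement on the arm, 0 to 4 per side |

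On the subject-level reading the path is open. Only the treated-area reading closes it sensibly, and the two neighbouring exclusions show that the protocol names the treatment area elsewhere when it means it.

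**Step 2. What does the score do there?** With no dimpling on either side at baseline, the likely rating is 0 on both sides and a difference of 0, whatever happens to laxity. Any other rating is hard to interpret as cellulite improvement.

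**Step 3. Size of the dilution.** Inputs:
- N = 24, the target sample size (Section 4A).
- f, the share of subjects treated on an area at stage 0-1. This is an assumption; the documents give no value.
- D, the mean difference among subjects treated where there is qualifying cellulite. It is left as a symbol because no effect size is stated.
- D0, the mean difference among affected subjects, assumed to be 0.

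Expected mean difference = (1 - f) × D + f × D0 = (1 - f) × D.

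| f (assumed) | Subjects affected, f × 24 | Expected mean difference | Reduction |
|---|---|---|---|
| 0% | 0 | 1.00 × D | 0% |
| 10% | 2.4 | 0.90 × D | 10% |
| 25% | 6 | 0.75 × D | 25% |

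The proportional fall equals f and needs no assumption about the standard deviation, a test or a significance level. If D0 lies between 0 and D, the reduction is smaller than f.

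**The case against.** The strongest reply is that the protocol probably means the treated area throughout. The four regions in inclusion criterion 2 are exactly the four that may be treated. Item 7 of the pre-treatment procedure records the stage straight after item 6 tapes the treated area, and it records the texture scale alongside, which exclusion criterion 3 applies to the area to be treated. An investigator applying exclusion criterion 1 to the proposed area would never take the path described. No sentence directs treatment of a stage 0-1 region. This is a fair account of the likely intent, and it limits the point to what the wording permits. It does not remove it, because the intent is not written and the choice-of-area rule offers laxity as a separate ground.

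Second, skin tightening is a declared aim in the title and the objective, so laxity is a deliberate cue. That stands, and in an area with both conditions it does no harm. It also makes the laxity route more likely to be used, while the efficacy score does not measure tightening.

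Third, a reader might infer a definite loss of power. With an assumed true effect of 0.60 SD, 24 pairs and a two-sided 5% paired t-test, power is about 80%. Holding the SD constant, it would appear to fall to 72%, 56% and 39% at f = 10%, 25% and 40%. That calculation contradicts its own premise: if affected subjects score exactly zero, the variance shrinks too, to (1 - f) + f(1 - f) × 0.60². Standardised effects are then 0.56, 0.50 and 0.43, and power is about 75%, 65% and 53%. More basically, Section 4A calls this a pilot with no basis for a significance calculation. The effect size, the test and every f are assumptions, so no power figure belongs in the conclusion.

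A reader might also infer that the control side must be at stage 2 or 3. The gap does not need that. The protocol means to treat the area with the most cellulite, so a milder control side is foreseeable, and barring it would be a new restriction.

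**Conclusion.** The point holds as a mismatch within the protocol: the choice-of-area rule, the eligibility criteria and the efficacy score are not tied to the same area. The text permits a subject to be treated and scored for cellulite on a region at stage 0 or 1. In such a subject the difference score is near zero or uninterpretable, and the efficacy estimate is diluted in proportion to f.

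The size rests on two assumptions: the value of f, and a zero difference in affected subjects. The documents do not show that f is above zero, and they set no limit on it. It would be wrong to read them as showing that such subjects will be enrolled, or that a planned power is lost. The point is worth correcting because analysis cannot restore cellulite to an area that had none, and because in a study of 24 a handful of such subjects would matter to the estimate.

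**What to change.** Reconcile Section 1, the design description and Section 4B as follows:

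1. Inclusion criterion 2: require stage 2 or 3 cellulite on the area to be treated.
2. Exclusion criterion 1: refer to that same area.
3. Choice of area: allow laxity to decide only among areas that meet inclusion criterion 2.
4. Baseline staging: state that the stage is recorded for the treated area, and record it for the opposite control area as well, without making the control area's stage an eligibility requirement. Any imbalance between sides can then be described.

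The cost is a few words in two criteria and in the choice-of-area sentence, plus one more recorded item. The stage is already assessed at screening. The downside is that a few candidates led by laxity become ineligible or are treated on a different region. Up to 40 may be consented for a target of 24, which leaves some room for this.
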